- All GP consultation records in the 12 months prior to diagnosis for children diagnosed with T1D
- All GP consultation records of the matched cohort of children without T1D. (This cohort will be matched on the date they presented to their GP with an acute illness. This will act as the time point for consultations in the previous 12 months.)

Within the consultation records variables will include:-

- Symptom details
- Diagnoses
- Tests undertaken
- Medication prescribed
- Co-morbidities

Demographic factors collected

- Children
 - Age at diagnosis
 - Gender
 - Deprivation quintile (based on postcode)
 - GP practices
 - List size
 - Number of GPs within the practice.

Initial analysis of the dataset will assess and explore the read codes attached to each GP consultation in the 12 months before diagnosis. The researchers will define the read codes and explore mechanisms for grouping symptoms to allow for meaningful clinical interpretation. Each patient's prodrome (the 12 months before diagnosis) will be assessed by analysing the number of GP visits, symptoms, diagnoses, tests undertaken and treatments given.

15 Statistical considerations

Randomisation

Not applicable

Sample size

As the primary purpose of this study is to seek an earlier diagnosis of T1D, the study is powered for the case-control study. Assuming a medium effect size (OR=1.5), a moderately low prevalence rate of the risk factor 30% in the control group, matching 3 controls per case and using a two sided 5% alpha and 80% power, we will require 322 children with T1D. If a total of around 390 children diagnosed with T1D were identified between 2010 and 2012 this would give the study over 90% power. A secondary aim of the study is to explore the risks associated with presenting in DKA (or not). Given that approximately 23% of children diagnosed with T1D are in DKA at diagnosis then we have 90 children in DKA and 300 not in DKA, we will not be powered to observe any small to medium effect sizes for any risk factors. This analysis will be exploratory in nature.

16 Analysis

Main analysis

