The two groups will be described using summary statistics (N (%), mean (sd), median (inter-quartile range)) for the explanatory variables identified as described above. Predictors of presenting in DKA at diagnosis (using the explanatory variables identified) will be examined using a two-level logistic regression model (children within practice). Where numbers allow, variation in DKA will be accounted and corrected for at the level of general practice. Associations between the prodromes for children presenting in DKA will be examined firstly at the univariable level and significant predictors (with a P-value <0.10) retained for the multivariable model. Odds ratios (ORs) will be estimated together with 95% confidence intervals (CIs).

The quality of the matching will be examined by describing the case-mix (with respect to age, gender, co-morbidites and practice factors) of the case (T1D) and control (general population of children) groups. The two groups will be also be described to examine any differences in prevalence of presentation of such symptoms, GP visits, tests and medications in primary care. A similar analysis will be used as in the T1D analysis only using a conditional logistic regression model to account for the non-independent observation created by matching, and results again presented as ORs alongside 95% CIs.

Data storage & retention

All data will be kept for 15 years in line with Cardiff University's Research Governance Framework Regulations for clinical research. This data will be stored confidentially on password protected servers maintained on the Cardiff University Network.

17 Study closure

The end of the study will be considered as the date of the submission of the final report.

18 Regulatory issues

Ethical and research governance approval

The study will be conducted in accordance with the recommendations for physicians involved in research on human participants adopted by the 18th World Medical Assembly, Helsinki 1964 and later revisions. The study will be submitted to an NHS Research Ethics Committee (NHS REC) for approval. This is consistent with the requirements of Cardiff University who will be requested to act as the study sponsor.

Consent

Informed consent will not be sought from participants, as the data being used is anonymised and patients who contribute to the Brecon Group register provide consent for their data to be used for research purposes.

Confidentiality

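### Section 16 screens symptoms together with the GP's responses to them into one multivariable model, so the adjusted OR of a symptom retained alongside its response is not its overall association

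*Protocol*

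**What the plan says.** Section 14 lists symptoms, diagnoses, tests, medication and co-morbidities as the variables taken from the consultation records. It says the 12 months before diagnosis will be assessed by "analysing the number of GP visits, symptoms, diagnoses, tests undertaken and treatments given". Read codes are to be grouped for clinical interpretation, but nothing separates what the child presented with from what the GP then did, and nothing orders the variables in time.

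Section 16 (Main analysis) then states the modelling rule. For DKA: "Predictors of presenting in DKA at diagnosis (using the explanatory variables identified) will be examined" by two-level logistic regression, with "significant predictors (with a P-value <0.10) retained for the multivariable model". For T1D cases against controls, the groups are described on "prevalence of presentation of such symptoms, GP visits, tests and medications in primary care", after which "A similar analysis will be used as in the T1D analysis only using a conditional logistic regression model". Results of both analyses are given as ORs with 95% CIs. There is one multivariable model per outcome, and the only stated entry criterion is the univariable P-value.

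**The concern.** The pooled variables are not parallel. A symptom is commonly the reason for a visit. A test, a working diagnosis or a prescription is commonly the GP's response in that consultation or the next. If a symptom and its response both pass the screen, the symptom's OR in the final model compares children with and without the symptom who had the same response.

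That is a different quantity from the one the research questions in section 4 point to. Question 1 concerns the number of and reasons for consultations, and question 2 the pathway that ends in DKA or not. The ultimate aim in section 5 is earlier diagnosis. A reader of the final table could conclude that a symptom carries no information about DKA when its association runs through whether it was acted on. This is separate from the merits of P-value screening, because it would remain if every candidate variable were kept.

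**Working it through.** The protocol gives no figure for this effect, so its size can only be illustrated. The one relevant figure is the DKA share in section 15: 23% of 390 is 0.23 × 390 = 89.7, which matches the stated 90. It is used below to check that the assumed inputs are realistic.

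**1. DKA model: the test as mediator.** Assumed inputs, none from the protocol: symptom recorded in 30% of children; tested in 70% with the symptom and 5% without; DKA risk 10% if tested and 27% if not; no direct effect of the symptom.

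- DKA risk with the symptom: 0.70 × 0.10 + 0.30 × 0.27 = 0.151.
- DKA risk without it: 0.05 × 0.10 + 0.95 × 0.27 = 0.2615.
- Overall risk: 0.30 × 0.151 + 0.70 × 0.2615 = 0.228, close to the protocol's 23%.
- Overall symptom OR: (0.151/0.849) / (0.2615/0.7385) = 0.50.
- OR within tested and within untested children: 1.00, because risk depends only on the test.

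With 50% tested among those with the symptom, the risk with the symptom is 0.50 × 0.10 + 0.50 × 0.27 = 0.185. The overall OR is then (0.185/0.815) / (0.2615/0.7385) = 0.64, again against 1.00 after adjustment.

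The value of 1.00 is built in by assuming no direct effect. Simulations with the symptom in 30%, tests in 30–60% with it and 2–5% without, and a test log-OR of −1.0 to −1.5 gave the following symptom ORs without and with the test in the model: 0.80 and 1.00; 0.61 and 1.01; 1.19 and 1.50; 0.89 and 1.49; 1.00 and 2.00. The last three include a direct symptom effect. In one of them (0.89 to 1.49) the direction reverses.

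**2. Does the P<0.10 screen keep both variables?** Datasets were simulated from the inputs in step 1, and the symptom and the test were each tested univariably at P<0.10.

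| Tested, given symptom | 390 cases | 3500 cases |
|---|---|---|
| 70% | both retained in about 79% (77–81% across runs) | 100% |
| 50% | both retained in about 47–50% | over 99% |

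Both sizes come from the protocol: 390 in section 15, and about 3500 in sections 8 and 14. Under these inputs the screen usually or often lets both through.

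**3. T1D case-control model.** A GP's test does not cause T1D, so there is no path from symptom through test to outcome. Take the exposure from section 15: 30% of controls and OR 1.5, giving 0.45/1.15 = 39.13% of cases. Keep testing at 70% with the symptom and 5% without, equal in cases and controls.

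- Tested stratum: (0.3913 × 0.70)(0.70 × 0.05) / [(0.6087 × 0.05)(0.30 × 0.70)] = 1.50.
- Untested stratum: the factors 0.30 and 0.95 cancel in the same way, giving 1.50.

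So adjustment leaves the OR unchanged. It moves only if testing, given the symptom, differs between cases and controls. For example, suppose that unrecorded severity makes the rate with the symptom 70% in cases and 50% in controls, with 5% otherwise. The OR becomes 1.5 × 0.70/0.50 = 2.10 among tested and 1.5 × 0.30/0.50 = 0.90 among untested children. A logistic model with symptom and test as main effects, fitted to the expected cells at 3:1, gives 1.09 against the overall 1.50. Matching was ignored here.

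**The case against.** The strongest case against has four parts.

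- **The final terms are not stated.** Entry depends on the screen, and grouping of codes comes first. A reader might infer that every symptom's OR will be adjusted for its own consequences. The text does not support that. It concerns only symptoms retained together with a response. Some tests or visits in a 12-month window will also precede a symptom or be unrelated to it. The rule itself is nevertheless written in section 16, so this is not merely detail left to an analysis plan.
- **Mediation cannot operate in the primary comparison.** This stands, as step 3 shows. Any distortion there needs a further link between testing or treatment and T1D. Such a link is plausible but is an added assumption.
- **The aims are association and prediction, and section 15 calls the DKA analysis exploratory.** Mutual adjustment is legitimate for prediction, so tests need not be banned as covariates. But section 16 reports ORs with CIs and no measure of predictive performance, so the ORs are likely to be read factor by factor. The exploratory label covers only the DKA analysis.
- **Univariable associations and descriptive prevalences are planned.** This helps, because comparing them with the adjusted ORs would reveal a shift. They are not adjusted for deprivation or earlier co-morbidity, however, and section 16 does not say that the univariable ORs will be reported alongside.

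**Conclusion.** The point holds in a limited form. Section 16 draws no line between presenting symptoms and the GP's response. An adjusted OR for a symptom retained with its response is therefore conditional on that response.

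For DKA this is adjustment for a mediator, and it can be large: 0.50 to 1.00, or 0.64 to 1.00, under the stated assumptions. For T1D against controls, the symptom OR is unchanged if testing depends only on the symptom, and is distorted only through unrecorded severity or other symptoms. The protocol fixes the size in neither analysis.

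A reader might go further and expect important symptoms to look null in the reported models. The documents do not support this. The null result in the DKA example follows from assuming no direct effect, other assumed inputs move the OR away from 1, and in the case-control model there may be no shift at all. Nor is mutual adjustment an error in itself. The error would lie in reading its symptom ORs as overall associations. The change is worth making because it is cheap and bears directly on both research questions.

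**What to change.** In section 16, for both the DKA analysis and the conditional logistic analysis, specify two models.

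1. **Symptom model.** Symptoms and reasons for consultation, adjusted only for factors that precede them: age, gender, deprivation, prior co-morbidity and practice, leaving out those already used for matching. State that these are the reported symptom ORs.
2. **Extended model.** Add visits, tests, working diagnoses and prescriptions. Label it as mutually adjusted or predictive, and state that its symptom ORs are not read as the symptom's overall association.

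The cost is a change of wording, a few extra fits on the same data, and two sets of ORs to present and explain. No new data extraction or change in sample size is needed.

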This is a case control study of a linked dataset (SAIL databank and Brecon Group database). Data from all children (15yrs and below) diagnosed with type 1 diabetes between 1st January 2000 to 31st December 2015 will be linked with the SAIL databank.

An anonymised data set will be created by the SAIL research analyst. This will include a cohort of matched controls who do not have T1D identified through the SAIL databank at a ratio of 3:1. The resulting dataset will contain all GP consultation records in the 12 months prior to diagnosis for children diagnosed with T1D, those diagnosed in DKA and a matched cohort of children without T1D.

Initial analysis of the dataset will use data mining techniques to assess and explore the read codes attached to each GP consultation. Further analyses will assess each patient's prodrome (12 months prior to diagnosis) by analysing the number of GP visits, symptoms, duration of symptoms, tests undertaken and treatments given.

7 Centre and Investigator selection

Not applicable

8 Participant selection

The first stage of the study will involve identifying all children (i.e. those under 15yrs of age) diagnosed with T1D from 1st January 2000 to 31st December 2015 in the Brecon Group Register and categorising

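### The univariable P<0.10 screen in Section 16 exaggerates the odds ratios it keeps and can drop confounders, mainly in the DKA model at about 390 children

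*Protocol*

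**What the plan says.** Section 6 starts from the records themselves: "Initial analysis of the dataset will use data mining techniques to assess and explore the read codes attached to each GP consultation". Section 14 adds: "The researchers will define the read codes and explore mechanisms for grouping symptoms to allow for meaningful clinical interpretation". The number of candidate variables is not given.

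Section 16 examines predictors of DKA in a two-level logistic model. Prodrome variables are tested one at a time, with "significant predictors (with a P-value <0.10) retained for the multivariable model". ORs with 95% CIs follow. For cases against controls, the same section says "A similar analysis will be used as in the T1D analysis only using a conditional logistic regression model", with "results again presented as ORs alongside 95% CIs". The protocol states no forced covariates, no shrinkage and no allowance for selection.

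Section 15 expects 90 children in DKA and 300 not, says this comparison lacks power for small to medium effects, and calls it exploratory. Section 14 expects about 3500 children, at least 700 of them in DKA.

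**The concern.** A variable reaches the final model only if its estimate in these data is far enough from 1. Where power is low, the estimates that clear that bar are mostly those that chance pushed outwards. Averaged over what is kept, ORs are too far from 1, and for weak factors the nominal 95% CI covers too seldom.

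The rule also judges a confounder by its own univariable P-value. That is not the right test of whether leaving it out shifts another factor's OR. Research question 1 asks about combinations of factors, and a univariable screen discards factors that matter only after adjustment.

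The results are meant to guide strategies for earlier diagnosis, so exaggerated ORs for particular symptoms or consultation patterns could misdirect them.

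**Working it through.** **1. The plan's own figure.** Section 15 gives the inputs: "Assuming a medium effect size (OR=1.5), a moderately low prevalence rate of the risk factor 30% in the control group", and "matching 3 controls per case and using a two sided 5% alpha and 80% power, we will require 322 children with T1D". Exposure in cases is 0.30 × 1.5 / (1 + 0.30 × 0.5) = 0.3913. The unmatched two-proportion formula gives 280 cases, or 294 with continuity correction. The matched formula with three controls per case gives 324 if the exposure correlation within matched sets is 0.2. The protocol states no correlation, so 0.2 is an assumption that comes close to 322. The point below does not depend on it.

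**2. DKA model, true OR 1.5, 30% exposure, 90 against 300.** For a 2×2 table, SE² is the sum of the reciprocals of the four expected counts.
- SE² = 1/35.2 + 1/54.8 + 1/90 + 1/210 = 0.0625, so SE = 0.250.
- P<0.10 needs |log OR| > 1.645 × 0.250 = 0.411, an OR of 1.51. An estimate above 1 must exceed the truth to be kept.
- u = (0.411 − 0.4055)/0.250 = 0.023, so P(kept) = 1 − Φ(0.023) = 0.491.
- Mean log OR when kept = 0.4055 + 0.250 × φ(0.023)/0.491 = 0.4055 + 0.250 × 0.3988/0.491 = 0.609, an OR of **1.84**. Simulation gives 1.83 to 1.85.
- CI coverage when kept = (0.491 − 0.025)/0.491 = 0.949. At this effect the fault lies in the estimate, not in the coverage.

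**3. Same comparison, true OR 1.2.** Exposure in the DKA group is 0.36/1.06 = 0.3396.
- SE² = 1/30.6 + 1/59.4 + 1/90 + 1/210 = 0.0654, so SE = 0.256. The cut-off is 0.421, an OR of 1.52.
- P(kept) = 0.1757 (upper tail) + 0.0092 (lower tail) = 0.1849.
- Mean OR when kept is 1.66 by formula and 1.64 to **1.65** by simulation.
- Coverage = (0.1757 − 0.0250)/0.1849 = 0.815; simulation gives **81%**.

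**4. Case-control model and larger sizes.** These use the same calculation on unmatched tables. At 390 against 1170, SE² = 1/152.6 + 1/237.4 + 1/351 + 1/819 = 0.0148 and SE = 0.122. The cut-off is 0.200, u = −1.68 and P(kept) = 0.954. The mean log OR when kept is 0.4055 + 0.1218 × 0.0966/0.954 = 0.418, an OR of 1.52. The other rows are simulated.

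| Comparison | True OR | Exposure | Mean OR when kept |
|---|---|---|---|
| DKA, 90 v 300 | 1.5 | 10% | 2.18 |
| DKA, 90 v 300 | 1.5 | 5% | 2.70 |
| DKA, N = 3500, 23% in DKA | 1.5 | 30% | 1.50 |
| DKA, N = 3500, 23% in DKA | 1.2 | 10% | 1.35 |
| DKA, N = 3500, 23% in DKA | 1.2 | 5% | 1.46 |
| Case-control, 390 v 1170 | 1.5 | 30% | 1.52 |
| Case-control, 390 v 1170 | 1.5 | 10% | 1.62 |
| Case-control, 390 v 1170 | 1.5 | 5% | 1.78 |
| Case-control, 390 v 1170 | 1.2 | 30% | 1.34 |
| Case-control, 3500 v 10500 | 1.5 | 30% | 1.50 |
| Case-control, 3500 v 10500 | 1.2 | 5% | 1.25 |

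**5. A dropped confounder.** All inputs here are assumptions: N = 390, about 23% in DKA, exposure and confounder each with OR 1.5, and exposure present in 15% of children with the confounder and 40% of those without. The confounder fails the screen in 65% to 66% of datasets.

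The rule as a whole gives a mean exposure OR of about 1.83 among datasets that keep the exposure, against about 1.47 from the full model over all datasets. That gap is the net effect of the rule and is mostly selection of the exposure. Confounding alone runs the other way in this example. If 40% of children have the confounder, its share is 0.06/0.30 = 0.20 among the exposed and 0.34/0.70 = 0.486 among the unexposed. Omitting it multiplies the OR by about (1 + 0.5 × 0.20)/(1 + 0.5 × 0.486) = 1.10/1.243 = 0.885, so 1.5 becomes about 1.33. With 30% or 50% prevalence the result is about 1.35 or 1.32. At N = 3500 the confounder fails the screen in only 2% of datasets.

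**The case against.** The strongest reply is that the DKA analysis, where the distortion is largest, is already called exploratory and underpowered. Losing a true OR of 1.5 about half the time is mostly low power: unscreened, it would reach P<0.05 in only 37% of studies. That stands. But the label corrects neither the ORs nor the CIs, and Section 15 applies it only to the DKA analysis.

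The reach of the rule is also less certain than it may look. The screening sentence speaks of prodromes, and Section 14 lists demographic factors separately, so screening of age, gender or deprivation is a plausible reading but not an explicit one. The same holds for carrying the threshold into the case-control model through a similar analysis. There, age, gender and practice are matched, and the opening of Section 14 adds socioeconomic class.

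Three stronger readings are tempting and not supported:
- A reader might infer that the screen raises the number of false-positive factors. It does not: a full model tests every null candidate at 5% too, and simulation shows no fewer false positives. That is ordinary multiplicity.
- A reader might infer that the data mining looks at case or DKA status. The protocol does not say so, and grouping codes for clinical interpretation can be done without it.
- A reader might infer that the primary results are generally inflated. At the design effect they are not.

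**Conclusion.** The concern holds in limited form. Because the protocol itself fixes the screen, this is not a detail left to a later plan. At 90 against 300 children it turns a true OR of 1.5 into about 1.84 among kept results, and 1.2 into about 1.65 with 81% coverage. It can also remove a confounder, which biases the exposure OR in a direction that depends on how the two are associated.

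In the case-control analysis the effect is negligible for OR 1.5 at 30% exposure and matters only for weak or rare factors. The size therefore depends on which of the protocol's cohort sizes applies: about 400 or 3500 children, and 90 or 700 in DKA. The figures assume binary factors and single unmatched tables; the confounder example rests on assumed associations. This should be changed, but it does not undermine the design.

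**What to change.** Delete the P<0.10 screen from Section 16. Define the clinical code groups without reference to case or DKA status, and say so in Sections 6 and 14. Fit one model per analysis containing all the code groups. Force age, gender and deprivation quintile into the DKA model, and deprivation into the conditional model if it is not a matching factor; Section 14 needs one matching list to settle that. State whether the case-control model follows the same rule.

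Whether the DKA model can carry every group depends on its size. With an assumed 25 terms, 700 events give 700/25 = 28 per term, but 90 give 90/25 = 3.6. If the model must be reduced at about 90 events, keep the forced covariates and use a shrinkage method.

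The cost is protocol wording, modest programming and slightly wider CIs. The covariates are already being collected. The full model does not reduce false positives, so multiplicity needs its own statement when results are interpreted.
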